6.1 Ublituximab

Dose modification of ublituximab is not permitted. Dose delays will be the primary method for managing ublituximab-related toxicities (see Table 3 below: Dose delay and modification schema for umbralisib and ublituximab). During infusion dose delays should follow the guidelines outlined in Section 5.2.2.

Supportive care should be provided and growth factor support should be applied as outlined in Section 5.3.

6.2 Umbralisib

Dose delays and modifications will be the primary method for managing umbralisib related toxicities. Ublituximab and umbralisib therapy should be held upon onset of any of the following toxicities until recovery as outlined in Table 3 below. Upon recovery of toxicities as outlined in Table 3 below, umbralisib dosing should be the initial drug restarted. Ublituximab infusions should restart at least 7 days after umbralisib dosing has resumed and there has been no recurrence of the toxicity. One exception to this rule, are any toxicities related to infusion reactions. Upon recovery of any Grade 3 or greater infusion related toxicities back to baseline of less than or equal to Grade 1, the requirement of 7 days of umbralisib dosing before ublituximab dosing can be waived in order to keep patients on schedule during the first cycle induction. During the first cycle, if there is a toxicity observed that requires holding of therapy that would cause the dosing of ublituximab to fall out of window or schedule, then that dose should be skipped, the patient should reinitiate umbralisib upon recovery and be dosed with ublituximab at the next scheduled infusion per protocol. If there is a recurrence of toxicity felt attributable to ublituximab then further ublituximab infusions may be stopped at investigator discretion.

Table 3. Hematologic Grading Scheme for subjects entering with abnormal platelets or hemoglobin.

Hematologic Grading Scheme	
Grade	Decrease in platelets¹ or hemoglobin² from pretreatment value
0	0-10%
1	10.01-24%
2	24.01-49%
3	49.01-74%
4	≥74.01%

1. Platelet counts must be below normal levels for Grades 1 to 4. If, at any level of decrease, the platelet count is < 20 x 10⁹/L (20,000/µL), this will be considered Grade 4 toxicity.

2. Hemoglobin levels must be below normal levels for Grades 1 to 4. Baseline and subsequent hemoglobin determinations must be performed before any given transfusions. The use of erythropoietin will not affect grading of toxicity and use should be documented

Table 4. Dose delay and modification schema for umbralisib and ublituximab.

NCI-CTCAE Grade	Dose Delay and/or Modification
Hematologic Adverse Event	
Neutropenia	
Grade ≤ 2 neutropenia	Maintain current dose and schedule of umbralisib and ublituximab (if applicable). Consider supportive care as warranted.
Grade 3 neutropenia	Maintain current dose and schedule of umbralisib and ublituximab (if applicable). Consider supportive care. If recurrence or persistent Grade 3, consider reducing umbralisib to next lower dose level at discretion of the investigator.

Grade 4 neutropenia or occurrence of neutropenic fever or infection	
Delay umbralisib and ublituximab (if applicable) until Grade ≤ 3 and/or neutropenic fever or infection is resolved; thereafter, resume umbralisib at current dose and schedule. Consider supportive care. If delay is > 56 days despite the use of G-CSF, discontinue umbralisib and, if applicable, ublituximab.
 
When/if restarting, restart ublituximab (if applicable) after 7 days of umbralisib dosing.
 
If recurrence after rechallenge, repeat these steps with allowance for reducing umbralisib to next lower dose level at discretion of the investigator.

	
If the absolute neutrophil count was $< 1 \times 10^9/L$ before therapy, the patient will not be evaluable for toxicity referable to ANC. The use of growth factors such as granulocyte colony-stimulating factor (G-CSF) is not relevant to the grading of toxicity, but should be documented. If a subject enters with a decreased ANC then any count < 500 should be considered as Grade 4 and managed as outlined above.

Thrombocytopenia	
Grade ≤ 3 thrombocytopenia	
Maintain current dose level and schedule of umbralisib and ublituximab (if applicable). Provide supportive care as clinically warranted.

Grade ≥ 3 thrombocytopenia with bleeding or Grade 4 thrombocytopenia without bleeding	
Delay umbralisib and ublituximab (if applicable) until Grade ≤ 3 without bleeding; thereafter, resume umbralisib at current dose and schedule. Consider supportive care intervention as warranted. If delay is > 56 days, discontinue umbralisib and, if applicable, ublituximab.
 
Restart ublituximab (if applicable) after 7 days of umbralisib dosing.
 
If recurrence after rechallenge, repeat these steps with allowance for reducing umbralisib to next lower dose level at discretion of the investigator.

Immune Related Pneumonitis*	
Grade 1 & 2	
Stop all therapy and hold until complete resolution. Restart umbralisib at one lower dose level. Restart ublituximab (if applicable after 7 days of umbralisib dosing). If delay is > 56 days, discontinue umbralisib and, if applicable, ublituximab.
 
If recurrence after re-challenge, discontinue all treatment therapy.

Grade ≥ 3	Discontinue all therapy

* For sinopulmonary infections clearly not related to immune-mediated pneumonitis, umbralisib may be continued at investigator's discretion. While pneumonitis has been

minimal with umbralisib, it is a reported adverse event associated with other PI3K delta inhibitors. Use of anti-pneumocystis and anti-herpetic viral prophylaxis is required.	
Diarrhea and/or Colitis	
Diarrhea Grade ≤ 2	
Maintain current dose and schedule if tolerable or hold umbralisib and ublituximab (if applicable); thereafter, resume umbralisib at current dose and schedule, and resume ublituximab (if applicable) after 7 days of umbralisib dosing.
 
NOTE: If persistent grade 2 diarrhea, despite supportive care, delay umbralisib and ublituximab (if applicable) until \leq grade 1; thereafter, resume umbralisib at current dose and schedule, and resume ublituximab (if applicable) after 7 days of umbralisib dosing. If recurrence after rechallenge, repeat these steps with allowance for resuming umbralisib at current dose or next lower dose level at discretion of the investigator.
 
If delay is $>$ 56 days, discontinue umbralisib and, if applicable, ublituximab. Restart ublituximab (if applicable) after 7 days of umbralisib dosing.

Diarrhea Grade 3	
Withhold umbralisib and ublituximab (if applicable) until Grade ≤ 2. Resume umbralisib at next lower dose level. If delay is $>$ 56 days, discontinue umbralisib and, if applicable, ublituximab.
 
Restart ublituximab (if applicable) at full dose after 7 days of umbralisib dosing.
 
If recurrence after rechallenge, repeat these steps with allowance for resuming umbralisib at next lower dose level at discretion of the investigator.
 
A diagnostic workup for Grade 3 diarrhea should be performed including a colonoscopy to evaluate for underlying colitis.
 
Monitoring of the patient should occur at least weekly until improvement and or resolution.

Diarrhea Grade 4	Discontinue all treatment, rechallenge prohibited.
Colitis Grade ≤ 3	
Hold umbralisib and ublituximab (if applicable). Treat with supportive care and after resolution of colitis, resume umbralisib at next lower dose level.
 
If delay is $>$ 56 days, discontinue umbralisib and, if applicable, ublituximab.
 
Restart ublituximab (if applicable) after 7 days of umbralisib dosing.

Colitis Grade 4	Discontinue all treatment, rechallenge prohibited.
Liver Toxicity (ALT/SGPT, AST/SGOT, Bilirubin, Alkaline Phosphatase)	
Grade 1	Maintain current umbralisib dose.

	
Assess concomitant medications and risk factors*. Monitor labs every 1-2 weeks.
 
Maintain full dose and schedule of ublituximab, if applicable.

Grade 2	
Maintain current umbralisib dose.
 
Assess concomitant medications and risk factors*.
 
Begin supportive care (prednisone 0.5-1.0 mg/kg/day or equivalent per investigator discretion) **.
 
Monitor labs at least weekly until Grade 1.
 
Once resolved to Grade ≤ 1, taper prednisone by 10 mg per week until off.
 
Maintain full dose and schedule of ublituximab, if applicable.
 
If liver toxicity recurs to Grade 2:
 
 ○ Re-initiate steroids. ○ Monitor labs at least weekly until Grade 1. ○ Consider delaying umbralisib. ○ If applicable, consider delaying ublituximab. ○ Once resolved to Grade ≤ 1 
 ○ If umbralisib was delayed, restart umbralisib at current dose. ○ If applicable: if ublituximab was delayed, restart ublituximab after 7 days of umbralisib dosing. ○ Taper prednisone by 10 mg per week until off. 
If umbralisib is delayed for > 56 days, discontinue umbralisib.
 
If ublituximab is delayed for > 56 days, discontinue ublituximab. Restart ublituximab (if applicable) after 7 days of umbralisib dosing.

Grade 3	
Delay umbralisib.
 
Assess concomitant medications and risk factors*.
 
Begin/continue supportive care (prednisone 0.5-1.0 mg/kg/day or equivalent per investigator discretion) **.
 
Monitor labs at least weekly until Grade 1.
 
Once resolved to Grade ≤ 1:
 
 ○ Restart umbralisib at one lower dose level. ○ Taper prednisone by 10 mg per week until off. 
If applicable, delay ublituximab until \leq grade 1; thereafter, resume ublituximab after 7 days of umbralisib dosing.
 
If umbralisib is delayed for > 56 days, discontinue umbralisib.

	If ublituximab is delayed for > 56 days, discontinue ublituximab. Restart ublituximab (if applicable) after 7 days of umbralisib dosing.		
Grade 4	Discontinue all treatment, rechallenge prohibited.		
* Assess for disorders of lipids and glucose, thyroid disorders, alcohol use, viral infections, etc.			
**Supportive Care – Aggressive management of lipid, glucose, other metabolic disorders, viral infections, etc.			
Important: Before initiating steroids, check for viral hepatitis or CMV infection.			
All Other Non-Hematological Adverse Events			
Grade ≤ 2	Maintain current dose level.		
	Withhold umbralisib and ublituximab (if applicable) until Grade ≤ 2 ; thereafter, resume umbralisib at current dose. If delay is > 56 days, discontinue umbralisib and, if applicable, ublituximab.		
Grade ≥ 3	Restart ublituximab (if applicable) at full dose after 7 days of umbralisib dosing. If recurrence after re-challenge, repeat these steps with allowance for resuming umbralisib at current dose or next lower dose level at discretion of the investigator.		
STUDY DRUG DOSE REDUCTION RECOMMENDATIONS			
Study Drug	Starting Dose	1st Dose Reduction	2nd Dose Reduction
TGR-1202	800 mg	600 mg	400 mg

A maximum of two dose level reductions are allowed for umbralisib. If a patient requires a dose reduction of umbralisib due to study drug related toxicity, the dose may not be re-escalated. If further evaluation of the toxicity reveals the event was not related to umbralisib, this must be recorded in the medical record and dose re-escalation to the next higher dose level may be considered at the discretion of the investigator and after discussion with the monitor.

7. Pharmaceutical Information

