5.2. Treatment Administration

All treatment will be administered on an outpatient basis. See section 5.2.1 and 5.2.2 for special precautions relevant for each specific study agent administration. All therapy will be administered in cycles with each cycle consisting of 28 days.

Enrolled subjects will initiate umbralisib monotherapy for a one cycle lead-in defined by Cycle -1. This cycle is designed to allow for correlative assay sample collection to assess early clonal shifts after umbralisib therapy. Without the lead-in these shifts may otherwise be masked by peripheral elimination of circulating tumor cells by anti-CD20 therapy. Subjects will be monitored closely upon initiation with a C-1D15 visit to assess tolerability of umbralisib monotherapy. Upon completion of Cycle -1 subjects will then continue on daily umbralisib and initiate combination therapy with ublituximab (U2). Ublituximab administration and induction/continuation is defined in Section 5.2.1. Ublituximab will only be administered through Cycle 6 (i.e no maintenance administration). Starting at C7D1 enrolled subjects will continue on umbralisib monotherapy. Umbralisib will be given on a continuous once daily basis starting at Cycle -1 for each 28 cycle until disease progression, discontinuation due to toxicity, subject death, subject withdrawal of consent, or investigator withdrawal. Administration schedule and timing of umbralisib administration in relation to ublituximab are further defined in Section 5.2.3. The overall treatment administration is depicted in the schema below Figure 1.

Subjects will be evaluated for objective response after completion of 6 cycles of combination therapy. Subjects with a response \geq PR will be allowed to continue on study (umbralisib monotherapy maintenance). A subject that does not meet objective response criteria by IwCLL 2018 guidelines outlined in Section 9.1 at C7D1 must be taken off study. See section 5.4.1 for further details in management of these subjects not meeting strict response criteria after completion of combination therapy.

Figure 1. Study Drug Administration Schema

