5.2.2 Management of Infusion Related Reactions

Since infusion-related hypotension may occur, antihypertensive medications should be held 12-24 hours prior to and throughout ublituximab infusion. Infusion related reactions including severe reactions have been reported with ublituximab administration in patients with CLL. Guidelines are provided below for patients who experience such reactions. Symptomatic infusion reactions, despite premedication, may be treated at the discretion of the treating physician, including but not limited to: oral acetaminophen 650 mg (or equivalent), corticosteroids, antihistamines, oxygen, and bronchodilators.

If an infusion related reaction is observed at any time during the ublituximab treatment, the treating investigator may reduce the infusion flow rate at their discretion.

The following are recommended infusion rate reduction/delay guidelines for patients who experience severe Infusion Related Reactions (IRR's) in which treatment should be interrupted. Final decision for infusion rate reduction/delay or discontinuation resides with the treating investigator.

1st or 2nd Infusion Interruption:

- Hold infusion and closely monitor patient, institute symptomatic medical management until resolution of IRR symptoms. Treating investigator must be notified by research team and documentation should occur in the patient chart.
 - Symptomatic medical management should include administration of acetaminophen, antihistamines, and/or corticosteroids for fever (temperature $>38^{\circ}\text{C}$) and/or chills
 - Physician may order meperidine for persistent rigors, caution to be exercised if

- patient is hypotensive and meperidine may contribute to ongoing hypotension.
- Administer antihistamines and/or corticosteroids for flushing, urticarial, pruritus, or angioedema
- Administer IV fluid boluses for hypotension
- Administer epinephrine, corticosteroids and antihistamines in the event of an anaphylactic reaction
- Following the judgment of the Investigator, and provided the patient is stable, the infusion may be resumed at half the previous rate.
- If the patient does not experience any further IRR symptoms, infusion rate escalation may resume at the increments and intervals as appropriate at the treatment cycle dose (see Section 5.2.1)
- For any Grade 4 infusion related reaction, ublituximab should be stopped indefinitely. Subjects that experience a Grade 4 infusion reaction will not be allowed to be rechallenged.

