3rd Infusion Interruption (same day):

- Discontinue infusion for that day – monitor patient for resolution of all symptoms. Patient should have all vital signs completed as well as any other standard of care procedures completed as warranted by the Investigator prior to release of patient from study site.
- Administer symptomatic medical management as above.
- Any remaining diluted investigational product should be discarded.
- If the infusion discontinued is the Cycle 1 Day 1 infusion, administer the scheduled Cycle 1 Day 2 dose according to the protocol dosing schedule.
- For any Grade 4 infusion related reaction ublituximab should be stopped indefinitely. Subjects that experience a Grade 4 infusion reaction will not be allowed to be rechallenged.

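### Section 6 restart wording for ublituximab (the Cycle 1 waiver in 6.2 and the Table 4 catch-all row) does not exclude Grade 4 infusion reactions, after which Section 5.2.2 forbids any further dose

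*Combined protocol and SAP*

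**What the plan says.** Section 6.2 first gives a general restart rule. After a toxicity that requires a hold, umbralisib restarts first, and ublituximab follows no sooner than 7 days later if the toxicity has not come back. Infusion reactions are the exception. The condition for the exception is "Upon recovery of any Grade 3 or greater infusion related toxicities back to baseline of less than or equal to Grade 1". When it is met, "the requirement of 7 days of umbralisib dosing before ublituximab dosing can be waived in order to keep patients on schedule" during Cycle 1. The same paragraph then covers a Cycle 1 ublituximab dose that falls out of window because of a hold: the dose is skipped and "the patient should reinitiate umbralisib upon recovery and be dosed with ublituximab at the next scheduled infusion per protocol". Neither sentence sets an upper limit on grade.

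Table 4 in Section 6.2 has no row for infusion reactions. Its catch-all row for other non-hematological events of Grade 3 or higher says to hold both drugs until Grade 2 or lower, resume umbralisib, and restart ublituximab at full dose after 7 days of umbralisib. It has no Grade 4 exception either.

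Section 5.2.2 states the Grade 4 rule twice. Under the first or second interruption: "For any Grade 4 infusion related reaction, ublituximab should be stopped indefinitely". Under the third same-day interruption: "reaction ublituximab should be stopped indefinitely. Subjects that experience a Grade 4 infusion reaction will not be allowed to be rechallenged".

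Two cross-references lead towards 5.2.2. Section 5.2 says "See section 5.2.1 and 5.2.2 for special precautions relevant for each specific study agent administration", and Section 6.1 sends the reader to 5.2.2 for dose delays that occur during an infusion.

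**The concern.** Waiving a wait before ublituximab only makes sense if ublituximab will be given again. By covering every grade from 3 upward, the 6.2 sentence names a grade at which Section 5.2.2 allows no further dose. The Table 4 catch-all row raises the same problem separately, because it gives a restart instruction for any event of Grade 3 or higher that has no row of its own.

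What is at stake is a patient-safety rule. Section 6 is where staff look up when to hold and restart drug. The likely error is that someone applies the waiver or the catch-all row without going back to 5.2.2. The waiver also applies in the cycle where reactions are most likely: Section 2.4.5 reports that 16 of the 23 infusion reactions in CD20-0703 followed the first infusion.

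**Working it through.** The plan states no figure on this point, so there is none to reproduce. The check compares Section 6 with Section 5.2.2, followed by a rough view of frequency.

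**Grade by grade**

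- *Grade 3.* Section 6.2 permits restart without the 7-day wait once the reaction is at Grade 1 or lower. Table 4 permits restart after the wait. Section 5.2.2 does not bar ublituximab. The sections do not conflict over whether ublituximab may be given.
- *Grade 4.* Section 6.2 as worded permits the same early restart, and Table 4 as worded permits restart at full dose. Section 5.2.2 stops ublituximab for good. The sections conflict.
- *Grade 5.* A fatal event cannot recover, so the recovery condition is never met.

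For infusion reactions, then, the only grade that the words after Grade 3 add is Grade 4, and there the waiver has no permitted use.

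**How Table 4 handles other Grade 4 events**

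Four toxicities in Table 4 lead to a permanent stop of all treatment at Grade 4: pneumonitis (from Grade 3 upward), diarrhea, colitis and liver toxicity. Infusion-reaction rows: 0. Elsewhere the table states its permanent stops explicitly. For infusion reactions a reader is left with the catch-all row and its restart instruction.

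**Whether the cross-references resolve it**

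The pointer in Section 6.1 concerns delays during an infusion. The waiver and the catch-all row concern restart after recovery, and Section 6.2 has no pointer to 5.2.2 for that. The pointer in Section 5.2 sits outside the dose-modification chapter. Within 5.2.2, the instruction to "administer the scheduled Cycle 1 Day 2 dose according to the protocol dosing schedule" stands beside the Grade 4 stop, but it applies only when a third same-day interruption has ended the Day 1 infusion.

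**Frequency (inputs from Section 2.4.5)**

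- CD20-0703, ublituximab alone: 16 Grade 2 + 7 Grade 3 = 23 reactions, which is all of them, so 0 were Grade 4 among 33 subjects. Exact two-sided 95% upper limit with 0 events: 1 − 0.025^(1/33) = 10.6%.
- UTX-TGR-103, the U2 combination: reactions of Grade 3 or higher in 1% of subjects. If that rate applied here, 24 × 0.01 = 0.24 subjects would be expected to have a reaction of Grade 3 or higher, and no more than that to have Grade 4.
- At the CD20-0703 upper limit, 24 × 0.106 = 2.5 subjects would have a Grade 4 reaction.

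These figures describe Grade 4 reactions. They do not describe barred doses, for which the documents give no rate.

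**The case against.** The strongest reply is that Section 6.2 governs when ublituximab restarts and Section 5.2.2 governs whether it may. On that view a timing waiver cannot reopen a drug that has been permanently stopped, and a careful reader would apply the bar. The phrase about dosing per protocol in 6.2 can also be read as carrying the bar with it. Much of this stands, and it is why the point is minor. It does not cure the text. Even on this reading the waiver has no use for a Grade 4 infusion reaction, and the Table 4 row is an instruction to restart, so the distinction between timing and permission does not help there.

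A second reply is that infusion related *toxicities* in 6.2 may be wider than infusion related *reactions* in 5.2.2. A Grade 4 cytopenia that accompanies a milder reaction could be restarted under Table 4, so narrowing the waiver would take something away. This is arguable. The loss would be small: the neutropenia and thrombocytopenia rows would still allow restart, with the ordinary 7-day wait.

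Two stronger readings are tempting, and the documents do not support them.

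- A reader might infer that 6.2 authorizes redosing after a Grade 4 reaction. It does not say so. It is permissive, it concerns timing, and 5.2.2 is explicit.
- A reader might infer that the bar in 5.2.2 is itself optional, because the section introduces its rules with "The following are recommended infusion rate reduction/delay guidelines for patients who experience severe Infusion Related Reactions" and leaves the final decision on discontinuation to the investigator. The ban on rechallenge is worded absolutely, and nothing in the discretion sentence makes an exception to it.

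**Conclusion.** The point holds as a minor safety-wording error. At Grade 4, the waiver in Section 6.2 and the catch-all row in Table 4 conflict with the permanent stop in Section 5.2.2, and the reference in Section 6.1 does not reach restart after recovery. The intended rule, no further ublituximab after a Grade 4 infusion reaction, is not in doubt. No endpoint, estimate or sample size changes.

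The conclusion assumes that the infusion toxicities in 6.2 include the infusion reactions in 5.2.2, which the exception's own introduction in 6.2 supports, and that an infusion reaction falls in the catch-all row because no other row fits it.

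The practical size is small. Grade 4 reactions are expected to be rare, although the CD20-0703 data alone cannot exclude a rate of up to 10.6%, and ublituximab was given there without umbralisib. A reader might want to count the infusions exposed to the error in each affected subject. The documents do not support a firm count, because it depends on when the reaction occurs and the Day 2 instruction in 5.2.2 covers only one kind of Day 1 interruption.

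**What to change.** Three edits, all required:

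1. In Section 6.2, limit the waiver to *Grade 3 infusion related reactions*.
2. Directly after it, add: *Grade 4 infusion related reactions: permanently discontinue ublituximab, no rechallenge, per Section 5.2.2.*
3. In Table 4, either exclude Grade 4 infusion related reactions from the restart instruction in the catch-all row, or add an infusion-reaction row that refers to Section 5.2.2. Without this edit the conflict remains in the table even after the paragraph is corrected.

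The cost is one changed phrase, one sentence, and one table row or clause at the next amendment. The waiver keeps its use at Grade 3, the intended rule does not change, and no procedures, visits or patients are added.

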3.2 Inclusion Criteria

A subject will be eligible for participation in the study if he/she meets the following criteria:

1. Subject must have confirmed diagnosis of CLL/SLL and a treatment indication based upon 2018 International Workshop on CLL (IWCLL) criteria.
2. Subject must have documented disease progression on a BTK and or BCL-2 containing regimen as the most recent prior line of therapy. Subjects who were treated with a regimen containing both classes of novel agents will be allowed to enroll and will be enrolled into Cohort B.

Subjects who receive a temporizing non-experimental treatment for up to 2 cycles such as monotherapy with an anti-CD20 monoclonal antibody or corticosteroids including high dose methylprednisolone immediately after progression on a BTK or BCL-2 inhibitor will be considered for enrollment after discussion with the study sponsor.

3. Subject must be ≥ 18 years of age.
4. Subject must have an Eastern Cooperative Oncology Group performance status of ≤ 2 .
5. Subject must have adequate bone marrow function and meet the below thresholds.

- a. Absolute neutrophil count of ≥ 750 cell/ μ L in absence of G-CSF for 7 days prior to enrollment.
 - b. Platelet count of $\geq 30,000$ cells/ μ L independent of transfusion for 21 days prior to enrollment
6. Subject must have adequate organ function and meet the thresholds below:
 - a. Total bilirubin ≤ 1.5 times the upper limit of normal (ULN). Subjects with bilirubin exceeding this limit due to Gilbert's disease are eligible.
 - b. Alanine aminotransferase (ALT) and aspartate aminotransferase (AST) $\leq 2.5 \times$ ULN if no liver involvement or $\leq 5 \times$ the ULN if known liver involvement
 - c. Creatinine clearance >30 ml/min/1.73m² as calculated by the MDRD equation.
7. Ability to swallow and retain oral medication.
8. Female subjects who are not of child-bearing potential (see Appendix: CONTRACEPTION GUIDELINES AND PREGNANCY), and female subjects of child-bearing potential who have a negative serum pregnancy test within 3 days prior to initial trial treatment. Male subjects of reproductive potential may not participate unless they agree to use medically acceptable contraception. Female subjects of child-bearing potential and all male partners, and male subjects must consent to use a medically acceptable method of contraception throughout the study period and for 4 months after the last dose of study drug.

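### Table 4 restarts umbralisib after a Grade 3 bilirubin event only at Grade 1 or lower, so an eligible Gilbert's subject back at an entry value above Grade 1 must stop treatment

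*Combined protocol and SAP*

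**What the plan says.** **Eligibility.** Section 3.2, item 6a (repeated in the Protocol Summary) limits total bilirubin to 1.5 x ULN and then makes an exception: "Subjects with bilirubin exceeding this limit due to" Gilbert's disease remain eligible. No cap applies to the exception.

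**Dose rules.** One block of rows in section 6.2, Table 4 covers four liver tests: "Liver Toxicity (ALT/SGPT, AST/SGOT, Bilirubin, Alkaline Phosphatase".
- Grade 2: umbralisib continues, labs are checked at least weekly until Grade 1, and prednisone is started at a dose given as 0.5-1.0 mg/kg/day or "equivalent per investigator discretion". At Grade 1 or lower the instruction is to "taper prednisone by 10 mg per week until off".
- Grade 3: umbralisib is held and restarted one dose level lower once the event is Grade 1 or lower. Ublituximab, if still due, is delayed to the same threshold and follows 7 days later. "If umbralisib is delayed for > 56 days, discontinue umbralisib"; the same limit applies to ublituximab.
- Grade 4: all treatment stops.

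No liver row or footnote mentions a baseline value. Section 12.2 names CTCAE version 4.0 as the grading scale. Its cut-points are not printed.

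**The concern.** The eligibility criteria let in subjects whose bilirubin is raised for a known reason, but the restart rule takes no account of that. If bilirubin is above Grade 1 at entry, the rule asks for a better value after a Grade 3 event than the subject had before the first dose.

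At stake is umbralisib for a subject whose liver event has resolved as far as it can. That can matter here: section 11.1 expects close to 90% of Cohort B to be double refractory, and section 5.4.1 recognises subjects who have no approved therapy of known efficacy. Ublituximab is at stake only for doses up to Cycle 6 Day 1.

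**Working it through.** The documents give no figure to reproduce. The check is a trace of the rules, followed by an illustrative size.

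**1. Trace.** Let *c* be the upper bound of Grade 1 for bilirubin and *b* the subject's entry value.
- Item 6a puts no cap on *b* in Gilbert's disease, so *b* > *c* is possible whatever *c* is.
- Bilirubin rises to Grade 3 and umbralisib is held.
- Bilirubin returns to *b*. Restart needs a value at or below *c*. Since *b* > *c*, the condition fails.
- The hold passes 56 days and umbralisib is discontinued.

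If *b* lies in Grade 2, the Grade 2 row applies from entry. Its weekly labs run to an endpoint that the subject may never reach, and any prednisone started has no taper trigger. Because prednisone is discretionary, this is a wording gap rather than a forced exposure.

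**2. Does other text rescue the subject?**

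| Place | What it covers | Reaches a bilirubin restart? |
|---|---|---|
| Table 3, "Hematologic Grading Scheme for subjects entering with abnormal platelets or hemoglobin" | platelets, hemoglobin | No |
| Table 4 neutropenia note: with low entry ANC, "the patient will not be evaluable for toxicity referable to ANC" | neutrophils | No |
| 6.2 text on recovery to baseline | infusion reactions, and still Grade 1 or lower | No |
| Table 4, other non-hematologic events (resume at Grade 2 or lower) | events without their own rows | No |
| Text after Table 4 on events not related to umbralisib | dose re-escalation | No |
| 11.4.1, resolution to baseline grade | length of off-study follow-up | No |

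The plan therefore adjusts for abnormal entry values in three blood counts, but not for the bilirubin that it expressly allows to be abnormal.

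**3. Ublituximab window.** Without delays, the last dose (Cycle 6 Day 1) falls on treatment day 28 + 5 x 28 + 1 = 169.

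**4. Illustrative size.** *p* = entry rate x Grade 3 liver rate x share of those events that fall on the test raised at entry. Expected number = 24*p*; chance of at least one = 1 - (1 - *p*)^24.

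Inputs:
- Entry rate: 1% to 10%, assumed.
- Share: 25% to 50%, assumed.
- Grade 3 rate: 3% or 10%, assumed from thresholds in section 2.4.5. No liver term appears there among Grade 3 or higher events above 3% on the doublet, and apart from neutropenia no Grade 3/4 event reached 10%.
- Entry status and Grade 3 events are taken as independent.

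| Grade 3 rate | *p*, low to high | Expected of 24 | At least one |
|---|---|---|---|
| 3% | 0.01 x 0.03 x 0.25 = 0.000075 to 0.10 x 0.03 x 0.50 = 0.0015 | 0.0018 to 0.036 | 0.18% to 3.5% |
| 10% | 0.01 x 0.10 x 0.25 = 0.00025 to 0.10 x 0.10 x 0.50 = 0.005 | 0.006 to 0.12 | 0.60% to 11.3% |

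The 10% row is hard to support for bilirubin. Section 12.1.3 puts treatment-related hyperbilirubinaemia, not limited by grade, between 1% and below 10% in 75 subjects on the doublet. Section 12.1.2 does not list bilirubin among related events of 2% or more in 136 subjects on umbralisib alone. In the other direction, the 3% and 10% thresholds apply to each event term and not to four tests together. Independence may also understate the risk, since a subject who starts high needs a smaller rise to reach a fixed cut-point. The table gives an order of magnitude, not a bound.

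**The case against.** **The strict limit may be deliberate.** No non-hematologic row in Table 4 offers a return to baseline. The protocol names hepatitis as a complication of PI3K-delta inhibitors (Protocol Summary and section 2.2), and it sets liver restart at Grade 1 or lower where other non-hematologic Grade 3 events need only Grade 2 or lower. This stands for ALT, AST and alkaline phosphatase. It is weaker for bilirubin in Gilbert's disease, where the plan itself waives the entry limit.

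**Attribution might remove the problem.** Section 6.2 speaks of umbralisib-related toxicity and section 12.2 allows an unrelated attribution, so an investigator could ascribe a fluctuation to Gilbert's disease. But 6.2 also tells sites to hold for any of the toxicities listed, and a drug-related rise on top of a Gilbert's baseline is not helped.

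**The grade cut-points are not in the documents.** True. The point is therefore conditional on entry above Grade 1, which the missing cap makes possible but does not show to be likely.

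**Stronger readings that a reader might infer.**
- *All four tests need a baseline rule.* Item 6b allows ALT/AST up to 5 x "the ULN if known liver involvement", and no alkaline phosphatase limit is set. Whether an eligible ALT/AST value exceeds Grade 1 depends on the unprinted ceiling: the range above it is 2.5, 2, 1 or 0 x ULN wide for ceilings of 2.5, 3, 4 or 5 x ULN. Relaxing these limits is a safety trade-off that the plan may have settled on purpose.
- *Only the test that triggered the event should have to recover.* Applied to everyone, that would allow restart after ALT recovers while bilirubin is newly raised. Nothing in the plan supports it.
- *Any liver event bars a Gilbert's subject from restarting.* Table 4 does not say whether its grades apply test by test. If they do, an ALT event in such a subject is unaffected.

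**Conclusion.** The concern holds in a narrow form. Followed exactly, Table 4 takes an expressly eligible Gilbert's subject off umbralisib after 56 days although bilirubin is fully back at its entry value, and no other text prevents this. Two conditions must be met: bilirubin above Grade 1 at entry, and bilirubin itself as the Grade 3 event.

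Severity is minor. Fewer than one affected subject is expected among 24 in every scenario shown, and the probabilities rest on an entry prevalence, a Grade 3 rate and a same-test share that the documents do not supply. A reader might infer that the efficacy results are at risk. They are not: no response-rate interval, sample size or time-to-event definition depends on this rule. It concerns the management of a single subject.

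**What to change.** Add one footnote to the Table 4 liver rows:

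*For subjects enrolled with Gilbert's disease and bilirubin above Grade 1 at entry, the Grade 2 bilirubin actions apply only to worsening from baseline, and for bilirubin the condition Grade 1 or lower is read as Grade 1 or lower, or return to the baseline value. All other liver tests must still be Grade 1 or lower before restart. Restart after Grade 3 stays at one lower dose level, with weekly labs continued.*

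The ALT/AST, alkaline phosphatase and Grade 4 rules stay unchanged, and no general test-by-test rule is added. The footnote should say which pre-dose draw is the baseline, because the chemistry panel is taken at both screening and Cycle -1 Day 1.

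The cost is one footnote and no new data. The downside is that a very rare subject restarts with bilirubin above Grade 1, at the known Gilbert's level and on a reduced dose.
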